Appendix 1: Schedule of Events

	Day 0 (In-Hospital, Baseline)	Day 1 , T1 (Discharge) (+30 days)	Week 1	Week 2	Week 3	Week 4 Day 30, T2 (+60 days)	Day 90 (+30 days), T3
Screening*	X						
Consent (a)*	X						
App Registration*	X						
Baseline Survey (b)*	X						
Usability Survey*							
T1 Survey (c)		X					
T2 Survey (c)						X	
T3 Survey (c)							X
Weekly Check-In (d)			X	X	X		
Data Entry (e)	X	X				X	X
AE/SAE assessment (f)	X	X				X	X
Survival Status (f)		X				X	X
End of Study (g)							X

- a) Patients may be approached and consented during their admission, if well enough; their hospitalization (e.g., while in step-down), or within 7 days of returning to their home for participation in the study.
- b) Completion of the baseline survey includes the patient providing self-reported information such as social and demographic information and general health status.
- c) Surveys 1, 2 and 3 will be completed via the app by all study participants, regardless of intervention combination assignments.
- d) For those participants randomized to 1 of the 8 intervention combinations, they will complete a weekly check-in to ascertain overall safety of the patient and usefulness of coping skills practice.
- e) AE/SAE assessment and survival status will be completed via EMR review and/or telephone interview.
- f) Study completion for patients enrolled in the study is considered to occur at the completion of T3. However, participants may undergo EOS if they are withdrawn from the study by the PI or opt to withdraw from the study voluntarily at any time. Should withdraw of a patient occur, the reason for withdraw and date of withdraw will be documented. AE/SAEs and survival status will be noted, as applicable.

*For aim 1 only.

Appendix 2: Study Workflow

Appendix 3: Randomization Arms

**Activity Log**

January 08, 2020 – [name] moved the SAP to this newly formatted file.

January 31, 2020 – Added table of statistical power; weaved in some of the text from the protocol paper

---

---

into the statistical analysis section. Added parameterization of the model and example SAS code.

July 20, 2022 – Added more information on sample size.

Now computing power for a range of effect sizes given 240 participants with 20% dropout (i.e., 192 participants after dropout).

August 5, 2022 – Adding section about minimization; adding notes about determining a threshold

June 23, 2023 – Clarifying that decisions will be made both in relation to effect size and p-value

June 29, 2023 – Updated data decisions regarding windows

August 22, 2023 – Updates to note that when PHQ-9 is the outcome, we do not adjust for PHQ-9 stratified; similarly for PHQ-10.

November 28, 2023 – Error fixed in power calculation simulation code. (Accidentally powered on T3 main effect due to confusion about naming of time points.)

---

# 1 Study Overview

As survival has improved for the 2 million people with cardiorespiratory failure managed annually in US intensive care units (ICUs), it has become apparent that these patients suffer from severe and persistent post-discharge symptoms of psychological distress including depression, anxiety, and post-traumatic stress disorder (PTSD). However, few targeted interventions exist that are relevant to patients' experiences and that accommodate their many physical, social, and financial barriers to personalized care.

Mindfulness is a practice of non-judgmental awareness that can alleviate distress by uncoupling emotional reactions and habitual behavior from unpleasant symptoms, thoughts, and emotions. Standard mindfulness training, typically provided face to face in group settings, has proven efficacious in improving psychological distress in various patient populations. However, in-person therapy is infeasible for the many ICU survivors with new disabilities, financial distress, and great distance from referral centers.

Therefore, we developed a telephone-delivered mindfulness-based training program for ICU survivors called LIFT and found that it was associated with improved symptoms of depression, anxiety, and PTSD in an uncontrolled pilot evaluation. Next, we adapted the LIFT program to a self-directed mobile mindfulness training app to overcome the inconvenience of scheduled weekly telephone sessions, and then compared it to telephone-based mindfulness and an education control in a pilot randomized controlled trial (LIFT1). This trial provided compelling evidence for the mobile mindfulness app's feasibility, adherence, retention, and clinically meaningful impact. It also showed how the LIFT program could be improved further by better targeting a population likely to respond, improving the app's delivery of content, and automating more features to improve user engagement.

Having addressed these gaps, we are now initiating a 2 x 2 x 2 factorial clinical trial (LIFT2) that is conceptualized as the Optimization Phase within the multiphase optimization strategy (MOST) framework. Through this trial, we will optimize mobile mindfulness by assessing three intervention components and their interactions. At the conclusion of this study involving 240 cardiorespiratory failure survivors with high levels of psychological distress just after hospital discharge, we will deliver a mobile mindfulness system fully optimized for usability, efficiency, scalability, and clinical impact that will be off-the-shelf ready for a next-step definitive RCT (LIFT3)—and can serve as a model for distance-based mind and body interventions.

The study time points are T1 (baseline & randomization), T2 (1 month post-randomization), and T3 (3 months post-randomization).

## 1.1 Statistical Aims

- Determine the effect of each of the three intervention components on change in PHQ-9 from randomization (T1) to 1 month post-randomization (T2).
- Assemble a multicomponent intervention package including the comparator level of components with main effect sizes of  $\geq 1.6$  units or  $p < 0.05$ . Otherwise, include the default level, unless interactions of  $\geq 1.6$  units (or  $p < 0.05$ ) are present that would cause us to include the comparator level.
- Use other qualitative and quantitative criteria to potentially reconsider decisions.

## 2 Study Population

### 2.1 *Inclusion Criteria*

See protocol.

### 2.2 *Exclusion Criteria*

See protocol.

### 2.3 *Sample size*

As described below, we need to have sufficient statistical power to detect main effects or interactions of at least 1.6 points on the PHQ-9—our decision-making benchmark. We calculated power for the test of a main effect or factor interaction in a constrained longitudinal model via simulation. Based on LIFT pilot data, the baseline standard deviation of PHQ-9 was assumed to be 5.3 and the covariance between time points ranged from 3.9 to 11.5 (**Table 1**). We examined a range of sample sizes at T2, from 120 participants up to 200 participants.

However, given our experience in a past psycho-behavioral intervention trial with nearly 40% dropout, we revised our target sample size to 240 total participants. By targeting 240 randomized participants, we will have ample power to detect factor main and interaction effects even with deviations from our assumptions (e.g., higher dropout rate, misspecified covariance matrix, etc.). We simulated 500 different datasets under several smaller effect sizes of PHQ-9 (**Table 2**). If our assumptions about dropout are correct, then we have 80% power to detect a main effect or interaction effect of 1.6 on the PHQ-9 scale. Appendix B displays the Stata code for simulating power.

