**Table 2. Power by PHQ-9 effect size (mean differences), N=192 participants after 20% dropout (recruited N=240)**

Regression coefficient	Effect size (mean difference)	Power
0.5	1.0	42.2%
0.55	1.1	47.8%
0.6	1.2	54.6%
0.65	1.3	61.2%
0.7	1.4	67.4%
0.75	1.5	75.4%
0.8	1.6	79.8%

\*Note that when using effect coding, the effect size is 2 times the regression coefficient. All effect sizes are on the nominal (unstandardized) scale.

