Given the factorial design, we will use effect coding, rather than dummy coding, for analyzing the effects of the intervention components. If the sample size is equal per condition, all of the tests of main effects and interactions are uncorrelated—that is, the main effect of a condition is the same even if other treatment conditions and interactions are included in the statistical model. Even with unequal sample sizes across conditions (as may occur with differential dropout by condition), if the imbalance is minor, the correlations between effects should be small.

Missing outcome data due to dropout or missing intermediate visits is expected to be at most 20%. Because the model will be fit using a full maximum likelihood method, we will be able to account for predictors of missingness in the model in order to obtain valid estimates of the main component effects, thanks to the property that the response can be missing at random (MAR) as defined by Little and Rubin. In practice, we will compare baseline characteristics of completers and non-completers. If we find that any covariates predict missingness, we will adjust for these variables in the model as a sensitivity analysis.

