## 6.2 Appendix B

### Stata code for simulation of power

```
/* Program to simulate data */
program powersimu, rclass
    version 16.0
    syntax, b1(real) [alpha(real 0.05)]

    clear
    set obs 192
    gen id = _n in 1/192

    *correlation matrix; estimates from PHQ-9 data from LIFT1 trial
    matrix V = (27.95, 9.67, 3.91 \ ///
                 9.67, 19.28, 11.54 \ ///
                 3.91, 11.54, 11.78)
    matrix list V
    matrix M = (0 \ 0 \ 0)

    *random effect drawn from a multivariate normal distribution
    drawnorm e1 e2 e3, means(M) cov(V)

    *check that the covariances line up with expected
    correlate e1-e3, covariance

    *set the 8 different intervention versions
    gen condition=1 in 1/24
    replace condition=2 in 25/48
    replace condition=3 in 49/72
    replace condition=4 in 73/96
    replace condition=5 in 97/120
    replace condition=6 in 121/144
    replace condition=7 in 145/168
    replace condition=8 in 169/192

    *set up the effect coded intervention components
    gen dose=1 if inlist(condition,1,2,3,4)
    replace dose=-1 if inlist(condition,5,6,7,8)

    gen symptoms = 1 if inlist(condition,1,2,5,6)
    replace symptoms = -1 if inlist(condition,3,4,7,8)

    gen call = 1 if inlist(condition,1,3,5,7)
    replace call = -1 if inlist(condition,2,4,6,8)

    *reshape to long format for fitting the statistical model
    reshape long e, i(id) j(time)

    *dummy code time
    replace time = time-1
    gen time1 = 1 if time == 1
    gen time2 = 1 if time == 2
    replace time1 = 0 if time1 != 1
    replace time2 = 0 if time2 != 1

    *rename variables for easier coding
    rename (dose symptoms call) (d s c)
    *note that t2 is the primary time point
    rename (time1 time2) (t2 t3)

    *generate interactions ahead of time
    gen ds = d*s
    gen dc = d*c
    gen sc = s*c
    gen dsc = d*s*c

    foreach x in t2 t3 {
        gen d`x' = d*x'
        gen s`x' = s*x'
        gen c`x' = c*x'
        gen ds`x' = d*s*x'
        gen dc`x' = d*c*x'
        gen sc`x' = s*c*x'
        gen dsc`x' = d*s*c*x'
    }

    *generate PHQ-9 with a main effect on dose at t2. All other effects are null.
    gen phq9 = 13+`b1'*dt2+0*st2+0*ct2+0*dct2+0*sct2+0*dsct2+0*dt3+0*st3+0*ct3+0*dst3+ ///
```

```

0*dct3+0*sct3+0*dsct3+e

*run mixed model with unstructured covariance on the residuals
mixed phq9 t2 t3 dt2 st2 ct2 dst2 dct2 sct2 dsct2 dt3 st3 ct3 dst3 dct3 sct3 dsct3 ///

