|| id:, noconst residuals(uns, t(time)) reml stddeviations

*obtain the p-value on the interaction of dose and T2
matrix a =r(table)
local p1=a[4,3]
return scalar pvalue=`p1'
*determine whether less than alpha
return scalar reject=(`p1'< `alpha')

end

/* Program to run the simulation multiple times */
capture program drop power_cmd_powersimu
program power_cmd_powersimu, rclass
version 16.0
syntax, b1(real) power(real) ///
[alpha(real 0.05) ///
 reps(integer 100) ]

*call the powersimu program
simulate reject=r(reject), reps(`reps') seed(12345): ///
powersimu, b1(`b1') alpha(`alpha')

quietly summarize reject

*return results
return scalar power = r(mean)
return scalar N = 192
return scalar alpha = `alpha'
return scalar b1=`b1'
end

/* Program to initialize parameters */
capture program drop power_cmd_powersimu_init
program power_cmd_powersimu_init, sclass
sreturn clear
sreturn local pss_numopts "b1"
sreturn local pss_colnames "b1"
end

/* Run the "program to simulate data" multiple times */
power powersimu, reps(500) b1(0.5(0.05)0.80) power(.80) ///
table graph(xdimension(b1) ydimension(power))

graph export "Power_Plot_PHQ-9_ES.emf", as(emf) replace
graph export "Power_Plot_PHQ-9_ES.pdf", as(pdf) replace

```

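### SAP 2.3 claims ample power despite higher dropout or a wrong covariance matrix, but at its own 1.6-point benchmark power is 79.8% at the assumed 20% dropout and about 67% at 40%

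*SAP*

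**What the plan says.** SAP section 2.3 opens with the requirement: "we need to have sufficient statistical power to detect main effects or interactions of at least 1.6 points on the PHQ-9", which it calls the decision-making benchmark. It explains the target of 240 randomised by past attrition: "given our experience in a past psycho-behavioral intervention trial with nearly 40% dropout". The robustness claim follows: "we will have ample power to detect factor main and interaction effects even with deviations from our assumptions". The examples of deviations given there are a higher dropout rate and a misspecified covariance matrix.

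The only power shown is for the assumed dropout. The text says "If our assumptions about dropout are correct, then we have 80% power to detect a main effect or interaction effect of 1.6", and the title of Table 2 reads "Power by PHQ-9 effect size (mean differences), N=192 participants after 20% dropout". Its last row gives 79.8% for 1.6 points. Appendix B fixes 192 participants and one covariance matrix. Section 4 of the SAP expects no more than 20% missing outcome data.

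The robustness sentence also stands in protocol section 9 (Sample Size and Power). There it follows a statement of more than 90% power for a 2-unit effect with 192 patients at T2. SAP section 4 says the threshold was later lowered from 2 to 1.6 units because the larger sample had raised power.

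**The concern.** Section 2.3 names one effect, 1.6 points, and the robustness claim is most naturally read as applying to it. At that effect the design only just reaches its nominal power when every assumption is met. The extra power from the larger sample was used to lower the benchmark, so it cannot also serve as reserve against attrition.

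A reader would conclude that the test of a benchmark-sized component tolerates dropout well above 20%, perhaps near the 40% that the paragraph cites. A component that fails the main-effect step stays at its default level unless an interaction or a later criterion changes the decision, and that package goes forward to the next trial.

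Loss above 20% is foreseeable from the documents. Protocol section 12 anticipates that most patients will complete visits outside the window, and SAP section 2.6 removes out-of-window measures. The protocol's own retention target at 3 months is 75%, although that concerns T3 and not the primary T2 time point.

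**Working it through.** **Inputs.** From the Appendix B matrix: T1 variance 27.95, T2 variance 19.28, T1–T2 covariance 9.67. Two-sided test at 0.05 (the code compares the model p-value with a default alpha of 0.05). Eight equal conditions, so each factor splits 1:1. The effect is twice the effect-coded coefficient (note to Table 2), so with balanced conditions the standard error is the same for main effects and interactions.

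**Formulas.** With complete data the constrained model tests T2 adjusted for T1:

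- Var(T2 | T1) = 19.28 − 9.67²/27.95 = 15.93
- SE of the mean difference = 2 × √(15.93/n)
- Power = Φ(effect/SE − 1.96)

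**The SAP's own figure.** At n = 192, SE = 0.576 and power for 1.6 points is Φ(1.6/0.576 − 1.96) = 79.3%, against 79.8% in Table 2. All seven rows of Table 2 reproduce within 1.5 percentage points. The Monte Carlo standard error with 500 replicates is √(0.798 × 0.202/500) = 1.8 points, so the method matches the SAP's.

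**Higher dropout**, with n = 240 × (1 − dropout):

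| Dropout | n | SE | Power, 1.6 points | Power, 2.0 points | Estimate needed for p < 0.05 (1.96 × SE) |
|---|---|---|---|---|---|
| 20% | 192 | 0.576 | 79.3% | 93.5% | 1.13 |
| 25% | 180 | 0.595 | 76.7% | 91.9% | 1.17 |
| 30% | 168 | 0.616 | 73.8% | 90.1% | 1.21 |
| 35% | 156 | 0.639 | 70.6% | 87.9% | 1.25 |
| 40% | 144 | 0.665 | 67.2% | 85.2% | 1.30 |

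A simulation of 20,000 datasets per row (T2 regressed on T1 and all seven factor effects) gave 79.2, 76.5, 73.3, 70.0 and 66.9% for 1.6 points, and 93.6, 91.8, 89.8, 87.7 and 85.0% for 2.0 points.

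**Size needed.** For 80% power at 1.6 points, n = 4 × 15.93 × (2.80/1.6)² ≈ 195.4, so 196 analysed. That allows 1 − 196/240 = 18.3% dropout. At n = 144 the effect detectable with 80% power is 2.80 × 0.665 = 1.86 points.

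**Covariance misspecification (assumed range).** If Var(T2 | T1) is 10 or 20% larger at n = 192, power for 1.6 points is 75.4 or 71.7%, and for 2.0 points 91.1 or 88.7%.

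**What could offset the loss.**

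- *T3 data (assumed range).* Suppose 25 or 50% of those missing T2 still give T3. The expected information from the three-time-point model with 240 at T1 then gives 78.5 or 80.2% for 1.6 points at 25% missing, and 70.9 or 73.9% at 40% missing.
- *Covariates.* To restore 80% they would have to explain 1 − n/195.4 of the residual T2 variance: 7.9, 14.0, 20.2 and 26.3% at 25, 30, 35 and 40% dropout.

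**The case against.** The strongest reply is that the sentence was written for the 2-point effect. It appears in the protocol directly after the 2-unit power statement, and in the SAP the next sentence turns to several smaller effect sizes, which implies a larger reference effect. For 2 points the claim is sound. The 80% figure for 1.6 is openly conditional on the dropout assumption, and no number in Table 2 is wrong. All of this stands, but section 2.3 itself mentions only 1.6 points, and the unconditional robustness sentence sits beside the conditional one without saying that it concerns a different effect.

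Other points stand in part:

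- The SAP says sample sizes from 120 to 200 at T2 were examined, which covers every n used here. The results by sample size are not shown.
- Covariate adjustment and T3 data would recover some power. With half of the T2-missing giving T3, 25% missing would be fully offset; 40% would not.
- Favourable covariance errors would raise power: about 87% if the T2 variance were 20% lower. A robustness claim has to hold for the unfavourable ones.
- At 25% dropout the loss is small, within about two Monte Carlo standard errors of the printed 79.8%. The case rests mainly on 30 to 40%.
- The decision rule is loosely worded. SAP section 1.1 includes a component if its effect is at least 1.6 units or p < 0.05, and otherwise keeps the default. Section 4 states the negation with another 'or', which could be read as making 1.6 binding. On that reading a true 1.6-point effect would be missed about half the time at any of these dropout rates. Section 1.1 supports the first reading, which is used here.

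**Conclusion.** The concern holds. At the SAP's own benchmark the design lacks the robustness that section 2.3 claims. On the SAP's assumptions the chance of missing a true 1.6-point main effect is about 21% at 20% dropout, 26% at 30% and 33% at 40%. The inclusion rule of 1.6 units or p < 0.05 does not soften this: p < 0.05 is reached at estimates of 1.13 to 1.30 points, below 1.6, so the p-value decides that step.

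These figures rest on the Appendix B matrix, balanced conditions, no covariates and no T2 information from participants who drop out. They describe the main-effect step only; interactions, T3, secondary outcomes and feasibility can still change the final package. The fault is confined to the robustness sentence. Table 2 is correct, and so is the protocol's power statement for 2 points.

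**What to change.** In SAP section 2.3, do one of the following:

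- limit the robustness sentence to the 2-point effect; or
- replace it with a table of power by dropout for 1.6 and 2.0 points, from Appendix B rerun at n = 180, 168, 156 and 144 beside the existing 192, with one further row for a larger residual T2 variance.

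In either case, state that on the simulation's assumptions power for 1.6 points is about 80% only if dropout is about 20% or less (196 analysed for a full 80%). State also that about 1.86 points is detectable with 80% power if dropout reaches 40%.

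The cost is one sentence, a short table and reruns of existing code. No extra patients are needed, and the design, the analysis and the protocol's power paragraph stay as they are. The one drawback is that the stated power looks less favourable.

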**Table 1. Assumed covariance matrix used to generate simulated PHQ-9 data**

	T1	T2	T3
T1	28.0		
T2	9.7	19.3	
T3	3.9	11.5	11.8

\*Note: values on the diagonals are variances; based on LIFT pilot data

**Table 2. Power by PHQ-9 effect size (mean differences), N=192 participants after 20% dropout (recruited N=240)**

Regression coefficient	Effect size (mean difference)	Power
0.5	1.0	42.2%
0.55	1.1	47.8%
0.6	1.2	54.6%
0.65	1.3	61.2%
0.7	1.4	67.4%
0.75	1.5	75.4%
0.8	1.6	79.8%

\*Note that when using effect coding, the effect size is 2 times the regression coefficient. All effect sizes are on the nominal (unstandardized) scale.

## 2.4 Randomization

The combination of the three factors each at two levels results in 8 experimental conditions. Allocation of the patients into one of the 8 experimental conditions (240 patients randomized with 30 in each condition) occurs at the time of T1 data collection completion (i.e., the first data collection after arrival home from the hospital). To ensure balance between the conditions on these important confounders, allocation is stratified by site (Duke, Colorado, Washington/Oregon), medical vs. surgical ICU vs. not applicable, depression symptom score at T1 (PHQ-9 < 15,  $\geq 15$ ), physical symptom score at T1 (PHQ-10 < 10,  $\geq 10$ ), and age (< 50,  $\geq 50$ ). Because of the large number of stratification variables relative to the experimental condition size, treatment assignment is conducted via a dynamic allocation minimization method. This algorithm is programmed directly within the LIFT mobile app platform.

## 2.5 Data Acquisition

*Fill in all relevant information:*

Study design	Factorial trial
Data source/how the data were collected	Primary data collection from participants in North Carolina, Washington, and Colorado
Contact information for team member responsible for data collection/acquisition	[name] [contact]
Date or version (if downloaded, provide date)	TBD
Data transfer method and date	REDCap to Box
Where dataset is stored	A Duke Box folder called PROJECT_DGHI_LIFT

## 2.6 Data Decisions

Per the protocol, all participants with measures out of window will be removed from the analysis. The windows are as follows:

Time Point	Window
1 month post-randomization (T2)	Up to 60 days post-randomization (+30 days from 1 month)
3 months post-randomization (T2)	Up to 120 days post-randomization (+120 days from 3 months)

Records outside of that window are identified in the final dataset using an indicator called “outofwindow”.

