For aims 1, 3 and 4 each participant will be asked to complete a singular study visit that will last approximately 30-60 minutes. During this study visit, post consent, the individual may be asked to do the following:

- Find and install the Pattern Health app (aim 1 and aim 4)
- Register to the LIFT2 study (aim 1 and aim 4)
- Complete baseline survey (aim 1 and aim 4)
- Randomize to 1 of 3 groups or screen fail purposely (aim 1 and aim 4)
- Audio-recording for interview using qualitative analyses (aim 3)
- Provide feedback on app content and usability (aim 1, 3, and 4)

For aim 2, each consented patient will be asked to complete up to four individual study visits.

- **Baseline:** this visit is to occur post-consent (same day, ideally) at the time of hospital admission just prior to discharge. However, this visit may occur at the time of hospital discharge within 7 days of returning to home. At this visit, the following will occur:
 - App Registration
 - Baseline Survey Completion
- **T1 (Day 0) (+30 days):** this visit is to occur at the time of hospital discharge to home, ideally within the first week (7 days) of returning to home; however, it can occur up to 1 month (30 days) from the time of hospital discharge to home. At this visit, the patient will complete the T1 survey via the app, which includes the PHQ-9, PTSS, PHQ-10, and MAAS surveys. Score dependent, the patient will be randomized to 1 of 8 intervention combinations. If the patient's psychological distress score is too low; he/she will receive an automated alert via the app describing they are not eligible and their study participation is complete.
- **T2 (Day 30) (+60 days):** this visit is to occur post 1 month randomization for those patients who remain eligible to participate in the study. PHQ-9, PTSS, PHQ-10, and MAAS surveys will be administered again. If the patient's survey scores indicate high levels of distress, as defined by a triggered SI alert or increased distress score from T1, a delegated study team member will contact the patient for safety precautions.
- **T3 (Day 90) (+30 days):** this visit is to occur post 3 months randomization for those patients who remain eligible to participate in the study. PHQ-9, PTSS, PHQ-10, and MAAS surveys will

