Analyses for Aim 1: After inclusion of Table 7's features in the mMT system, we will employ a user testing analytic approach guided by Usability.gov guidelines and our past studies.^{3,4,26} We will conduct in-person interviews among enrolled individuals identified by stratified purposive sampling with characteristics that could impact usability (~25% ≥age 65, ~25% <high school education, ~25% with low technology confidence).^{27,29}

Participants will complete: (1) a 'think aloud' protocol in which coordinators record patient comments as they use mMT;³⁰ (2) Systems Usability Scale (SUS);²⁸ (3) all system

tasks, and (4) a semi-structured interview. In a parallel approach, staff will test the screening and randomization system using a series of 100 simulations, aiming for 100% success in correct and equal randomization to Aim 2's factor conditions. We will organize any identified problems with Nielsen usability heuristics to guide subsequent revisions.³¹ Based on our past work,^{3-5,14,15} we anticipate 2-5 cycles of 2-5 participants each will be sufficient to reach a target of 'excellent' usability (i.e., mean SUS score ≥85)^{26,32} as well as to ensure confidence in the screening system's feasibility.

Analyses for the trial (Aim 2): The main goal of our intention-to-treat analyses is to estimate main effects and interactions of combined experimental conditions to be able to determine which LIFT use case is best. That is, would LIFT impact be greater by accepting the "high" level of a factor instead of the simpler default "low" level of the factor. Our overall analytic approach will be guided by frameworks presented by Collins and Collins & Kugler.^{33,34} To understand general patterns in the data, we will first calculate raw means, medians, and measures of variability at each time point for the primary and secondary outcomes. These will be grouped by the main effect of each factor (e.g. standard versus high-dose), collapsed over the other factors. We will also examine these descriptive statistics by groups as defined by the two-way and three-way interactions of the factors.

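### SAP 2.6 removes participants rather than records when a measure is out of window, so read literally a late T3 deletes an on-time T2; the T2 limit also differs (SAP day 60, protocol day 90)

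*SAP*

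**What the plan says.** **Removal rule.** SAP 2.6 reads "Per the protocol, all participants with measures out of window will be removed from the analysis". After the window table it adds "Records outside of that window are identified in the final dataset using an indicator called" outofwindow. The first sentence acts on people and the second on records.

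**T2 window.** SAP 2.6 gives "Up to 60 days post-randomization (+30 days from 1 month"). Protocol section 7, Study Visits, gives "T2 (Day 30) (+60 days"), and Appendix 1 repeats it as "Day 30, T2 (+60 days").

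**T3 window.** The protocol has Day 90 with a 30-day allowance. SAP 2.6 has "Up to 120 days post-randomization (+120 days from 3 months"), in a row labelled T2.

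**Analysis.** Protocol section 9 states: "The main goal of our intention-to-treat analyses is to estimate main effects and interactions of combined experimental conditions". SAP section 4 uses the same label. It models PHQ-9 at T1, T2 and T3 jointly with an unstructured covariance and relies on maximum likelihood under missing at random for absent responses. The primary outcome is PHQ-9 at T2 (SAP 3.1).

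**The concern.** The removal sentence decides who enters the primary analysis, and two competent programmers could build different datasets from it. Under the literal reading, someone who answered T2 on time but T3 after day 120 loses every score. Survey timing at T3 is a post-randomization behaviour. Using it to exclude people from the T2 comparison departs from intention to treat, costs precision, and can bias the T2 component effects in some circumstances. The model gives no reason to do this, because a participant with T1 and T2 but no T3 is an ordinary partial record.

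The T2 limit is a separate matter. It decides whether primary-outcome surveys completed on days 61-90 count at all, and the two documents give different answers.

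**Working it through.** **1. Unit of removal.** The flag in SAP 2.6 could be used to drop flagged records or to drop anyone who has a flagged record. The SAS code in SAP Appendix A runs on a dataset called analysis and never mentions outofwindow, so whichever choice is made happens upstream, unseen. Nothing else in the SAP states the unit.

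**2. T2 window.**
- Protocol: 30 + 60 = day 90. SAP: 30 + 30 = day 60. Days 61-90 are in dispute.
- The protocol's plus sign is an increment, not an end day. At T1 it is Day 0 with 30 days, explained as "it can occur up to 1 month (30 days) from the time of hospital discharge to home". At T3 it is 90 + 30 = day 120, which equals the SAP's T3 limit.
- The SAP's T3 bracket would give 90 + 120 = day 210, against its own day 120. With the T2 label on that row, this is clerical.

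**3. The plan's own power figure.** The inputs come from SAP Appendix B: Var(T1) = 27.95, Cov(T1,T2) = 9.67, Var(T2) = 19.28, N = 192, two-sided alpha 0.05. The effect is 1.6 points (SAP 2.3). Covariate adjustment is ignored.
- Var(T2 | T1) = 19.28 - 9.67²/27.95 = 15.93
- SE of a main effect = 2 × √(15.93/192) = 0.576
- Power = Φ(1.6/0.576 - 1.96) = 79.3%, against 79.8% in SAP Table 2. The figure reproduces.

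**4. Power under each rule.** The documents give no rate of late surveys, so 10/20/30% of the 192 is an assumption. Participant removal uses SE = 2 × √(15.93/N). The T2-record column sums the information from complete participants and from those with T1 and T3 only.

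| Late share | N left, participant removal | SE | Power, participant removal | Power, late T3 record dropped | Power, late T2 record dropped (T3 kept) |
|---|---|---|---|---|---|
| 10% | 172.8 | 0.607 | 75.0% | 79.3% | 77.5% |
| 20% | 153.6 | 0.644 | 70.0% | 79.3% | 75.2% |
| 30% | 134.4 | 0.689 | 64.2% | 79.3% | 72.5% |

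Dropping only T3 costs nothing at T2, because T3 has its own effects in the model and adds no information on T2 once T2 is observed.

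These losses come on top of 20% dropout: 172.8, 153.6 and 134.4 are 72%, 64% and 56% of 240. If dropout were 10% and a further 10% were late, N = 240 × 0.9 × 0.9 = 194.4 and power is 79.8%, so there is no shortfall.

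**5. When participant removal biases T2.** Assume a true T2 effect of zero, late shares of 10% in one factor level and 20% or 30% in the other, and odds of lateness rising 1.5, 2 or 3 times per SD of T2 PHQ-9.

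| Odds ratio per SD | 10% v 20% late | 10% v 30% late |
|---|---|---|
| 1.5 | 0.14 | 0.28 |
| 2 | 0.23 | 0.45 |
| 3 | 0.32 | 0.64 |

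Entries are PHQ-9 points, favouring the level with more late surveys. The bias is 0.00 when late shares are equal (10% v 10%, with the same relation to PHQ-9 in both levels). It is also 0.00 when lateness depends only on T1 PHQ-9. If T3 is the late survey, dropping only that record gives 0.00 in all six cases. If T2 is the late survey, dropping only that record still leaves 0.06-0.28 when T3 is observed, and as much as participant removal when T3 is absent too.

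**The case against.** The strongest reply is that record-level removal is what was meant. The flag is on records, the model takes partial data, SAP section 4 expects missed intermediate visits, and protocol section 7 keeps terminated participants in the analysis up to the point of exclusion. This stands as evidence of intent, but it does not change what the removal sentence says. A record flag can equally be used to select people for removal. If that was the intent, the correction is one word.

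The illustrated loss may also be too large. The loss-to-follow-up rule in protocol section 7 turns many non-responders into dropouts, who are already within the planned 20%, and the shares above are added to that 20%. This stands, and the power figures are illustrations only. A reader might infer heavy loss from protocol section 12, which expects most patients to miss visit windows. That remark covers all visits, concerns deviation reporting and gives no T2 or T3 rate.

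A reader might also infer that a survey on days 61-89 cannot be classed as a late T2 or an early T3. The documents do not support this. T2 and T3 are separate app surveys, and the protocol's T3 window opens at Day 90 with no early allowance. What is open is whether the SAP counts such a T2 survey.

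Finally, the supplied protocol contains no rule removing out-of-window data, so a reader might conclude that the SAP's attribution is false. That goes too far. The SAP relies on a separate protocol paper (SAP 3.5), and its activity log records a decision on windows on June 29, 2023. The gap supports asking for the source and no more.

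**Conclusion.** The point holds on two counts that can be read from the text. The removal sentence names participants and, followed literally, deletes on-time primary outcomes when T3 is late. The T2 upper limits differ by 30 days. Neither shows that any on-time T2 score has been or will be deleted; the documents leave that open.

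The size is conditional. With 10-30% of the 192 late at T3 (assumed), power for 1.6 points is 75.0% down to 64.2% under participant removal, against 79.3% under T3-record removal. There is no shortfall if dropout and removals together stay within 20%. It is tempting to read the rule as biasing the T2 effect in general, but bias requires lateness that is related to follow-up PHQ-9 beyond T1 and that also differs by factor level. Nothing in the documents indicates differential lateness. The 0.14-0.64 points show what could happen under those assumptions, set against a 1.6-point decision benchmark.

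This should be settled before the analysis dataset is built.

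**What to change.** - In SAP 2.6, replace participants with records. Only the out-of-window measure is set to missing; every randomized participant and all their other PHQ-9 records stay in the planned constrained longitudinal model.
- Reconcile the T2 upper limit between protocol section 7, protocol Appendix 1 and SAP 2.6.
- Cite the source of the removal rule, or delete its attribution to the protocol.
- Add one sensitivity analysis that includes late T2 records, using the existing outofwindow flag.
- Clerical: correct the label and the bracket in the SAP's T3 row.

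The cost is SAP wording and one extra model run. There are two downsides. Record removal still loses late T2 scores and can leave some bias when T2 lateness depends on the T2 score itself. The sensitivity run addresses that case but widens assessment timing: if PHQ-9 shifts by an assumed 1 point over the delay, a 10-20 percentage-point difference in late share between factor levels adds 0.10 × 1 to 0.20 × 1 = 0.1-0.2 points.
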